# 3.2 Secondary Endpoints/Events/Outcomes

Secondary aims: To examine intervention effects on the following family- and child-level outcomes:

- 1) Home availability of healthful foods and beverages and quality of those served at family meals and snacks.
- 2) Children's dietary intake (e.g., calories, fruits and vegetables, sugar-sweetened beverages).
- 3) Children's minutes of moderate-to-vigorous physical activity and sedentary behavior per week, particularly screen time.

# 4.0 Study Interventions/Interactions

## 4.1 Description

VERSION DATE: 4/22/19

The research design includes qualitative research and a randomized controlled trial. We will be conducting the research in several stages.

Stage 1: Planning and adaptation (months 1-12). Stage 1 will focus on establishing a Steering Committee (larger community group) and an Action Team (specific team of community partners to put decisions into action). These groups will use a Community-Based Participatory Research (CBPR) approach to adapt the HOME Plus program (shown to be effective in an urban community) for a rural community. Members of the Action Team will meet monthly for the first year to determine how to adapt the HOME Plus program for rural families. During committee meetings, community assets will be mapped to facilitate buy-in and ensure inclusion of necessary partners, and assess and finalize our strategies. A logic model of the relationships between program resources, activities, outputs and outcomes will be created using a graphical depiction to address needs of the rural communities and facilitate implementation and uptake.

An ongoing evaluation of the extent to which CBPR principles are followed will be conducted. Thus, we will develop guidelines to describe the academic/community partnership and how decisions were made. Committee members will complete a CBPR survey that assesses decision-making processes for: 1) participant involvement, 2) shaping the purpose/scope of research, 3) research implementation and context, and 4) nature of research outcomes. (Change in protocol to submit survey items and Action Team Consent Form approved 10/12/16.) Committees will also use a RE-AIM framework to assess Reach, Effectiveness, Adoption, Implementation, and Maintenance to address real world contexts of research translation.

Stage 2: Randomized controlled trial (Years 2-5). Planning will be followed by a randomized controlled trial (RCT) in rural New Ulm. Participants will include 120 7-10 year-old children and their primary meal-preparing parent/guardian.

Study participants will be recruited using multiple methods. Recruitment will be conducted by UMN staff and community partners, including area schools, Allina Health, New Ulm Medical Center physicians, UMN Extension Service, Brown County Public Health and community organizations. We will use direct mailing, flyers, presentations and other public announcement delivery channels. At some events, families will be given a small trinket to increase interest in learning about the program. Trinkets will be of minimal monetary value (\$1.00 or less) and will include items such as fruit and vegetable stress balls, pens, note pads, jump ropes and indoor Frisbees. Current study participants will also be contacted and asked to share approved study flyers with any friends who they think might be interested in the study. All recruitment materials will direct interested families to contact the Evaluation Director by phone for eligibility screening. Study staff will also be available to screen interested families in person at recruitment events. An open access website page will house study information for potential participants and control group families to facilitate recruitment for the RCT. As part of our recruitment strategy, we will use personal health records available to a study Co-Investigator ([name], a community partner from Allina Health who was awarded a subcontract) to identify potentially eligible participants for a recruitment mailing. The UMN academic researchers on the team will not have access to PHI. [name] will access medical records at the New Ulm Medical Center to identify parent names and addresses of children who are eligible to

VERSION DATE: 4/22/19

participate in the NU-HOME study (i.e., they will be 7-10 years old). This information will only be used to send an introduction letter (from Allina Health) about the study and invite the parent to participate. [name] will not send PHI to the UMN researchers and it will not be retained as research data.

Participants will complete measurements at three time points: baseline (before randomization), at post intervention (8-10 months after randomization) and at follow-up (14-16 months post randomization). At baseline, adult participants will provide written consent for participation and children will provide written assent. Data collection will be conducted in a quasi-group format (individual families working with individual staff) in convenient community locations, simultaneously. Based on our previous work, baseline assessments should take 1.5-2 hours, with shorter subsequent assessments. Trained study-staff will measure the height and weight of the adult and child participants. Online surveys will be completed on an electronic device (laptop, ipad, phone) by the adult participant to assess household level data (e.g., home food availability, family meal frequency and environment, nutritional quality of foods served at meals and snacks) and individual-level data (physical activity, usual fruit and vegetables intake). The parent and child will also participate in two interviews about the food the child ate in the past 24-hours. (Change in protocol from child interview to parent and child interview and from three to two interviews was approved 4/24/17.) The child will also wear an accelerometer to assess their physical activity. The child participant will also complete surveys to assess individual level data (e.g., fruit and vegetable preferences). Children will also complete two additional midpoint measurements.

During the two additional short data collection visits, child participant's height and weight will be measured and they will answer questions about physical activity, particularly at school, and healthy eating. (Change in protocol for additional child measurement was approved 4/24/17.) Children will be measured after school, removed briefly from class during school or measured at their home. Principals have provided support for measuring students at school and parents will be notified in advance of the measurements by text, email, or letter (depending on their preferred method of communication).

Following baseline data collection, families will be randomized to the intervention program (NU-HOME; n=60 families) or a delayed intervention (n=60 families) in a staggered cohort design (two cohorts). The 7-month NU-HOME program aims to prevent childhood obesity by actively engaging children and parents/guardians to prepare regular, nutritionally-sound and appropriately-portioned snacks and meals eaten together and by reducing sedentary behavior, particularly screen time. The NU-HOME intervention program will promote physical activity through the existing programs of our community partners and resources in the community as well as through the study website. The 7-month intervention will be delivered to multiple family groups in convenient community settings. Intervention families will participate in seven monthly, two-hour sessions. All household members will be invited to participate in the sessions, as the inclusion of the entire family will facilitate comprehensive support for increasing the healthfulness of the home environment. Sessions will include an introduction and food preparation with all family members, separate adult and child sessions, and end with concluding statements, home activity assignments and enjoyment of a large group "family meal." The Research Team will develop a website for intervention participants. (Change in protocol to provide UMN accounts for intervention participants on secure UMN website developed specifically for the NU-HOME study was approved 10/2/17.) Intervention families will be allowed access with a secure, password

VERSION DATE: 4/22/19

protected login. They will have access to sessions that will be augmented online and will cover session content, video demonstrations and session materials (e.g., recipes) for both parents and children. The Research Team will coordinate with Heart of New Ulm (HONU) webmasters to link the NU-HOME website to the HONU main webpage after the research is complete. Intervention staff will establish and maintain rapport with families in sessions and will support families by phone four times during the intervention. Calls will use established protocols to employ motivational interviewing techniques such as reflective listening, agenda setting, and eliciting change talk to set goals and support behavior change and self-monitoring. All data collected as part of these calls will be entered in a secure REDCap database.

Stage 3 (Year 5): Delayed intervention. Our program design includes a wait-list control group and a "train the trainers" model to facilitate good will, stakeholder satisfaction and sustainability. Wait-list control group families will be able to receive the NU-HOME program after follow-up data collection.

Stage 4 (Year 5): Dissemination. The dissemination phase will begin with meetings between the Steering Committee, Action Team and Research Team to decide on timing of and venues for dissemination. We expect venues will include traditional academic journals, research conferences, technical and lay reports (to parents, health care professionals, stakeholders), local non-research conferences at schools, community events, and media.

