**HOME Plus full-scale trial.** The recently completed full-scale HOME Plus study RCT (intervention and attention-only control) with 160 families (8-12 year-old child and parent/guardian) was conducted in urban communities using a staggered cohort design (two cohorts) ([name] et al., 2014). Eligibility included child BMI>50th percentile; English literacy; no plans to move within 6 months; and no severe medical conditions prohibiting study participation. Recruitment and baseline assessments occurred in summers of 2011 (Cohort 1) and 2012 (Cohort 2), followed by randomization (n=81 intervention families, n=79 control families). Participants were representative of the larger county; 71% white (child), 44% overweight/obese (child), 35% household received economic assistance, with full representation of the economic range; however, HOME Plus parents were more likely to have a college degree (61%). Data collection was very successful with 100% compliance at baseline, 93% retention at post-intervention and 89% at follow-up (21-months post randomization). Each assessment included psychosocial surveys and anthropometry (parent and child), puberty assessment (child), three 24-hour dietary recalls (child), home food inventory (parent), and a family meal inventory of 7 dinners (parent). Families randomized to the intervention attended 10 monthly sessions delivered by trained interventionists to multiple family groups (approximately 5-10 families) in community settings. Other family members also attended sessions or childcare (75% of families brought additional family members). The intervention focused on experiential activities and included parent discussion groups, hands-on nutrition activities, taste-testing, and family meal preparation. Participation was high with 68% of families attending at least 7 of 10 inperson sessions and 84% completing at least 4 of 5 goal-setting calls which used motivational interviewing techniques. Families randomized to the control group received monthly newsletters with healthful eating tips. The intervention had a promising reduction in excess weight gain when treatment groups were compared for the entire sample. Moreover, given the influence of puberty on weight gain, post-hoc stratification analyses were conducted to assess effects on BMI-z-scores by pubertal onset; findings indicated a statistically significant pubertal onset-by-treatment group interaction at both post-

VERSION DATE: 4/22/19

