## 9.3 Screening

For Cohort 1, interested individuals will call the Evaluation Director to be screened for eligibility. She will describe the study, answer any questions, and ask additional questions to determine eligibility based on inclusion and exclusion criteria. For Cohort 2, attempts are being made to increase the diversity of the study sample. Flyers will be distributed in both English and Spanish. The flyers in Spanish will direct interested families to a bilingual staff member who will screen them for eligibility. For Cohort 2, study staff will also be available at community events to screen interested families in person. Families will be offered small trinkets to increase interest in learning about the research study. Trinkets will be of minimal monetary value (\$1.00 or less) and will include items such as fruit and vegetable stress balls, pens, note pads, jump ropes and indoor Frisbees.

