#### 12.4 Recruitment Materials

We will use direct mailing, flyers, presentations and other public announcement delivery channels. Current study participants will also be contacted and asked to share approved study flyers with any friends who they think might be interested in the study. (Change in protocol in which we submitted final recruitment materials was approved 3/27/17.) (Change in protocol submitted 3/20/2018 for recruitment materials for Cohort 2 with names of both major towns included in Cohort 2 as well as a Spanish version of the flyer). Families will be offered small trinkets to increase interest in learning about the research study. Trinkets will be of minimal monetary value (\$1.00 or less) and will include items such as fruit and vegetable stress balls, pens, note pads, jump ropes and indoor Frisbees.

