#### 17.0 Data Management

#### 17.1 Data Analysis Plan

Analysis plan. The analysis plan integrates our theoretical framework for behavior change and our temporal design. The analysis plan includes descriptive analyses, assessment of

VERSION DATE: 4/22/19

primary and secondary outcomes, and testing of potential moderation and mediation effects using an intent-to-treat methodology.

Descriptive analyses. Baseline participant characteristics will be reported using means and standard deviations or median for continuous measures and frequencies for categorical measures. To examine group comparability at baseline, differences between intervention and wait-list controls will be assessed using chi-square tests for categorical data or two-sample t-tests for comparisons of continuous data. Descriptive statistics of all outcome measures will be calculated at each assessment period. Inter-item correlations and internal consistency measures (i.e., Cronbach's alpha) will also be calculated.

Primary outcome analyses. For the analysis of the primary outcome of child BMI, a two-step approach will be used. First, two-sample t-tests will be used to assess potential changes in age- and gender-adjusted child BMI z-scores from baseline to post-intervention (i.e., immediate change). Second, baseline-adjusted analysis of covariance while adjusting for child age, gender, race and economic assistance will be performed. Analyses of associations with overweight status will be conducted with multivariate logistic regression while adjusting for baseline BMI z-scores or BMI z-squared to allow for curvature. Sustained program effects will be assessed using a similar approach with follow-up BMI z-scores.

Intent-to-treat principle. All comparisons will be performed under the intent-to-treat principle (i.e., all randomized participants will be included and analyzed according to group assignment, regardless of compliance). A 5% two-sided type I error rate will be used to determine statistical significance. SAS software version 9.4 (SAS Institute Inc., Cary, NC, USA) will be used for statistical analyses. Because the intervention is delivered in multiple family groups, we anticipate group facilitation effects (i.e., participants have greater benefits than if the intervention were delivered individually). Thus, we will investigate intraclass correlations (ICCs) in the test for intervention effectiveness.

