Secondary outcome analyses. Secondary outcomes will be analyzed using the same approach as with the primary outcome. In addition, to compare study groups over time, linear mixed models with baseline measures, group, and time (baseline, post-intervention and follow-up) as fixed covariates will be fitted. Group by time interactions will also be introduced. Transformation will be considered to ensure data normality. Other potential covariates (i.e., gender, age, education level, rural code) will be entered in models, if necessary. These models will assess between-group effects following randomization, within-group changes, and whether changes in the outcomes from baseline to post-intervention or to follow-up differed between the groups (group x time interaction). Based on preliminary studies, we expect that intervention families will have changes in food availability and intake, physical activity and sedentary behaviors after receipt of the NU-HOME program that will remain consistent at follow-up.

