#### 17.2 Power Analysis

Power calculations are based on two assessment time points, correlation over time, and variability of age- and gender-adjusted BMI z-scores. We propose to recruit 120 families (one eligible child and one parent per family) to allow for a 15% attrition rate with a final effective sample of about 100 families in the study by the end of follow-up. Using child (<11 years old) data from the HOME Plus trial, we estimated a within-child correlation (p) between the primary outcome measurements over time of 0.9. Utilizing a baseline-adjusted analysis approach, with a sample size of 96 (48 per group), we will be able to detect an

VERSION DATE: 4/22/19

effect size (ES) of 0.25 for age- and gender-adjusted BMI z-scores at 80% power. This effect size corresponds to approximately 1.4 kg decrease in average weight gain between intervention and control groups. This corresponding decrease was estimated using BMIi=M(1+LSzi)1/L formula with age-and gender-specific L,M,S parameters and average weight and height values for 8-10 year old boys and girls [at 50th or higher percentile for weight].

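### Randomisation runs in two cohorts recruited in successive years, but cohort is in no planned model: a cheap, minor precision gain, provided the allocation ratio is the same in both cohorts

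*Combined protocol and SAP*

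**What the plan says.** Section 4.1 (Stage 2) randomises after baseline, 60 families to the programme "or a delayed intervention (n=60 families) in a staggered cohort design (two cohorts"). Section 25.0 has Cohort 1 recruited in study year 2 and Cohort 2 in year 3. Only the overall 60:60 split is given. No section states the ratio within a cohort or mentions stratification.

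The cohorts are not recruited alike. Section 9.3 says: "For Cohort 2, attempts are being made to increase the diversity of the study sample". Section 12.4 refers to "recruitment materials for Cohort 2 with names of both major towns included in Cohort 2 as well as a Spanish version of the flyer". Section 12.5 adds, for Cohort 2 only, a prize draw at post-intervention tied to actigraph wear time and a gift card for the interim child measurement.

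Section 17.1 gives the primary analysis as a two-sample t-test of change in BMIz, after which a "baseline-adjusted analysis of covariance while adjusting for child age, gender, race and economic assistance will be performed". Follow-up is handled similarly. Secondary outcomes use the same approach plus linear mixed models, for which "Other potential covariates (i.e., gender, age, education level, rural code) will be entered in models, if necessary". Cohort appears in none of these, nor in the logistic model for overweight status, nor in the power analysis of section 17.2.

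**The concern.** The two cohorts differ in calendar year, in outreach and, for activity monitoring, in measurement incentives. If children in one cohort have systematically higher BMIz at 7 months after adjustment for baseline and the listed covariates, that difference stays in the residual when cohort is omitted.

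The consequence depends on how arms are spread across cohorts, which the plan does not say.

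- **Balanced within cohort:** the cohort difference cancels from the treatment contrast, but the model still counts it as noise. Standard errors are slightly too large and the test is slightly conservative.
- **Same ratio, but balance left to chance:** the test keeps its size and loses a little power.
- **Ratio differs by cohort:** cohort becomes a confounder.

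Baseline BMIz, race and economic assistance (and rural code in the secondary models) may partly stand in for cohort, but none of them identifies it.

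**Working it through.** **Inputs from sections 17.1 and 17.2:** 48 children per group, correlation 0.9, effect size 0.25 (outcome SD 1), two-sided 5%.

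**Assumptions, not in the documents:** two cohorts of equal size; residual cohort gap d of 0, 0.1 or 0.2 SD after covariate adjustment; 0.436 taken as the within-cohort residual SD.

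**1. The plan's own figure.** Residual SD s = sqrt(1 - 0.9²) = 0.436. SE = 0.436 × sqrt(2/48) = 0.0890. 0.25/0.0890 = 2.810. Power = Φ(2.810 - 1.960) = 80.2%. The stated 80% is reproduced.

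**2. Inflation of residual variance when cohort is omitted.** k = 1 + (d/2)²/s², with s² = 0.19. This gives k = 1, 1.0132 and 1.0526 for d = 0, 0.1 and 0.2; sqrt(k) = 1, 1.0066 and 1.0260.

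**3. Arms balanced within cohort.** The true SE stays at 0.0890, but the reported SE is multiplied by sqrt(k).
- Power without cohort = Φ(2.810 - 1.960 × sqrt(k)).
- Type I error without cohort = 2 × (1 - Φ(1.960 × sqrt(k))).
- Power with cohort = Φ(2.810 - 1.960) = 80.2%.

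**4. Same ratio, arms not balanced within cohort.**
- Power without cohort = Φ(2.810/sqrt(k) - 1.960).
- With cohort in the model, chance correlation between arm and cohort costs a variance factor of about 1 + 1/93, so power = Φ(2.810/sqrt(1 + 1/93) - 1.960) = 79.8%.

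| Gap d (SD) | Balanced: without → with | Change | Type I error without | Not balanced: without → with | Change |
|---|---|---|---|---|---|
| 0 | 80.2% → 80.2% | 0 | 5.0% | 80.2% → 79.8% | -0.4 |
| 0.1 | 79.9% → 80.2% | +0.4 | 4.85% | 79.7% → 79.8% | +0.1 |
| 0.2 | 78.8% → 80.2% | about +1.5 | 4.4% | 78.2% → 79.8% | +1.6 |

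Changes come from unrounded values; for example, 80.23 - 78.78 = 1.45.

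**5. Break-even when arms are not balanced.** k = 1 + 1/93 gives d = 2 × 0.436 × sqrt(1/93) = 0.09 SD. Below that gap, adding cohort loses a fraction of a point.

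**6. Unequal cohorts.** With a share p in one cohort, (d/2)² becomes p(1-p)d², which is smaller. For a one-third/two-thirds split at d = 0.2, k = 1 + (2/9)(0.04)/0.19 = 1.0468. The gain falls to 1.3 points (balanced) or 1.4 points (not balanced).

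**7. Simulation.** 60,000 runs per setting, two cohorts of 48, ANCOVA on baseline, t reference. At d = 0.2, power without and with cohort was 77.4% and 79.0% (balanced), and 76.6% and 78.4% (not balanced). At d = 0 and not balanced it was 78.9% and 78.4%. Levels are 1 to 1.5 points below the formula in both models; the differences agree. The mean estimate was 0.2496 to 0.2502 for a true 0.25 in every setting.

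**8. If the ratio differed by cohort.** Suppose 30:18 in one cohort and 18:30 in the other, with d = 0.2. Omitting cohort shifts the estimate by 0.2 × (30/48 - 18/48) = 0.05 BMIz in size. Simulated type I error was about 7.4%, against 5.0% with cohort in the model. A mild 26:22 / 22:26 split did not inflate it (4.0% to 4.6% when cohort explained 5% to 20% of residual variance).

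**The case against.** The strongest reply is that nothing is broken. The planned ANCOVA is valid, the sample size reproduces, and the gain rests on a cohort gap that the documents do not give. In three of the six settings the change is -0.4, 0 or +0.1 points. The evidence for a residual gap is also thin. Spanish flyers and wider outreach affect who enrols, and race, economic assistance and baseline BMIz are already in the primary model. In-person screening is tied to Cohort 2 in section 9.3 but appears without that limit in sections 4.1 and 12.1. The wear-time draw applies to both arms and has no evident link to BMIz; it could matter only for activity outcomes, whose variance the documents do not give.

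Most of this stands and keeps the point minor. It does not remove it: cohort is a known feature of the randomised design, and the plan should say how it is handled. Settling it now also avoids a later discretionary choice, since the secondary covariates enter only if judged necessary.

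Three stronger readings are tempting but unsupported.

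- **Omission biases the result.** That needs markedly different ratios across cohorts, and nothing in the documents suggests them.
- **Omission is harmless whatever the allocation.** That needs the same ratio in both cohorts, which is not stated either.
- **The power figure already contains the cohort gap, so adding cohort would lift power above 80.2%.** The plan says that from "data from the HOME Plus trial, we estimated a within-child correlation", and that trial "was conducted in urban communities using a staggered cohort design (two cohorts"). But the plan does not say whether 0.9 was computed within or across cohorts, and that trial's cohort variance is not the gap between these two cohorts.

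**Conclusion.** The point holds as a minor, inexpensive improvement. Cohort is part of the randomised design and is absent from the planned models. With the same allocation ratio in both cohorts, the linear analyses are unbiased and type I error does not exceed 5%. What is lost is a little precision: at most about 1.5 points of power (balanced) or 1.6 points (not balanced) at an assumed gap of 0.2 SD with equal cohorts, and less with smaller gaps or unequal cohorts. The power calculation that "with a sample size of 96 (48 per group), we will be able to detect" the stated effect is not wrong.

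The reassurance about bias and type I error is conditional on equal ratios and on linear models. In the logistic model for overweight status, omitting a prognostic cohort moves the conditional odds ratio slightly towards 1 without inflating type I error; that is a matter of which odds ratio is targeted, so the proposal stays with the linear models. Clustering by session group in the intervention arm is a separate matter that a cohort term does not address.

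**What to change.** Add two statements to section 17.1:

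1. Cohort (1 or 2) is a prespecified fixed effect in the primary ANCOVA, at post-intervention and follow-up, and in the linear secondary models. For the cohort-adjusted effect, the conclusion rests on this ANCOVA and not on the unadjusted t-test of change.
2. The allocation ratio within each cohort, and whether arms were balanced within cohort.

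The second statement lets a reader confirm that the condition for no bias is met. If the ratios did differ, the cohort term would prevent the resulting bias and inflated type I error.

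The cost is one degree of freedom and no new data. The downside is about 0.4 to 0.5 power points if there is no cohort gap and arms are not balanced within cohort, and essentially nothing if they are balanced.
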